7.1 Schedule of events

Please refer to the table in Section 7.1.1 for the schedule of events.

Study Visit	Screening Visit 0	Observation (seven day prior to baseline)	Baseline Visit 1	Week 4 Visit 2
Window (days):			+/	28 +/- 3 days

Type of Contact:	Office	Home	Office	Office
Informed consent	X			
Eligibility assessment	X			
Demographics, including smoking & alcohol history	X			
Complete medical history	X			
Prior/Concomitant therapy	X		X	X
Vitals			X	X
Physical examination			X	
PROMIS-Fatigue short form	X		X	X
Physician's Global Assessment			X	X
Patient's Global Assessment			X	X
PROMIS -29			X	X
HAQ-DI/SHAQ			X	X
QUIDS-SR			X	X
Raynaud and digital ulcer VAS			X	X
Raynaud's phenomenon diary			X ^c	X
Assess for Adverse Events			X	

Timing of assessments

If not stated otherwise, all assessments and procedures will be performed by or under the supervision of an investigator.

For timing of assessments and procedures, please refer to Section 7.

7.1.2.1 Visit 0 – Screening

Screening evaluations will be performed only after the participant has provided written informed consent. The following evaluations will be performed and information obtained up to 28 days before the baseline visit.

- Participant information and obtaining of written informed consent
- Eligibility: Assessment of inclusion and exclusion criteria (see Section [5.1](#))
- Demographic data, including sex, race, ethnic group, year of birth, smoking history and alcohol consumption
- Medical and surgical history
- Prior and concomitant therapy
- Medication history

7.1.2.2 Visit 1 – Baseline

The following assessments will be performed at the Baseline visit

- Reconfirmation of eligibility
- PROMIS-fatigue scale administered
- Patient reported outcomes (QUIDS-SR, patient global assessment, PROMIS-29, HAQ-D1/SHAQ, visual analog scales) and physician global assessment
- Vital signs (blood pressure and heart rate). The blood pressure is measured in a sitting

position after the participant has been at rest for at least 5 minutes. The same arm is always used for these measurements

- Digital ulcer assessment
- Assessment of Raynaud attacks – participant provided the one-day diary and RCS to complete the day following the screening
- Recording and assessment of AEs (see Section [7.5.1.3](#))
- Downloading of the mobile application and teaching of how to use the Apollo wearable device. The participants will be allowed to use it up to 30 minutes to familiarize themselves with the working of the device while at this visit.

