4. STUDY DESIGN

4.1 Design overview

This clinical trial is a single-center, open-label, single-arm study of 30 individuals with SSc and fatigue.

The study will allow for subjects to continue standard of care medications for the management of SSc as background therapy.

The study design consists of a single, four-week intervention. The screening and baseline visits can be combined when the screening is not able to be performed over the phone in advance.

- **Screening phase:** up to 4 weeks prior to baseline visit
- **Observation period:** During this one week phase participants will track their daily Raynaud attack frequency and duration using a diary. This will occur in the seven days preceding the baseline intervention phase.
- **Open-label intervention phase:** This consists of a four-week period during which participants will use the Apollo wearable system as needed to manage symptoms including fatigue. During the intervention phase participants may use the wearable at their discretion and control. Participants will track their daily Raynaud attack frequency and duration using a diary during week 4 of Apollo use. Participants will complete questionnaires on day 1 of the open-label and intervention phase, and at their follow-up four weeks later.

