4.1.1 Screening phase (up to 4 weeks prior to baseline visit)

After providing written informed consent, participants will undergo a screening evaluation to determine their eligibility (see Section [7.1](#) for a detailed schedule of events). Participants will complete the PROMIS-Fatigue scale to determine if they have moderate to severe fatigue. If a T score of 45 is obtained, and all inclusion criteria are met, then the patient may proceed to the observation phase. Participants will be given the 7-day diary to be completed starting one week prior to their scheduled baseline visit. They will be reminded by telephone call or text (based on

their preference) to begin their diary collection.

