4.1.2 Intervention Phase

At the baseline visit, participants who have met all of the inclusion criteria. At this visit they will complete the following questionnaires:

- 1) PROMIS-fatigue
- 2) PROMIS-29
- 3) The QUIDS-SR
- 4) HAQ-DQ with SHAQ
- 5) Raynaud condition score, Raynaud visual analog scale and digital ulcer visual analog scale

They will then be provided the wearable Apollo system device. They will download the mobile application, and be taught how to install it and use it to control the wearable Apollo device by the research coordinator(s). Any questions will be answered at this time. Participants will be able to use the device from the time they leave the visit. Use of the device will be entirely at the subject's control.

In the week prior to their end-of-study visit, participants will complete a daily diary collection of Raynaud attack episodes and symptoms using the paper diary form. This will be provided prior to leaving the baseline visit.

Participants will be sent a reminder call or text the day before and day they are to begin their diary collection on one week prior to their scheduled end-of-study visit.

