7.6 OTHER PROCEDURES AND VARIABLES

7.6.1 Raynaud's attacks assessment

Raynaud's attacks will be assessed using the composite of the following 6 individual outcome measures in order to minimize the measurement variability and placebo response(7): Raynaud's condition score, patient assessment of Raynaud's phenomenon, physician assessment of Raynaud's phenomenon, attack symptoms, duration of attacks, and number of attacks per day.

The Raynaud's condition score is a daily patient assessment of Raynaud's phenomenon activity using a 0-10 ordinal scale. It incorporates the cumulative frequency, duration, severity and impact of Raynaud's phenomenon attacks, reflecting the overall degree that Raynaud's has affected use of the participant's hands. The Raynaud's condition score, along with details of the frequency and duration of Raynaud's attacks, will be incorporated into the daily diary that participants will be asked to complete for 1 week (7 days) at the time points shown below.

The patient and physician assessment assesses the severity of Raynaud's phenomenon in the past week using a 0-100 VAS.

Frequency: The diary is to be completed by participant for one-day during the observation period, and one-day at the end of study (to occur the day prior to end of study visit).

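### Section 7.1.2.2 issues the baseline Raynaud diary at Visit 1 for a day that, with separate visits, is already past or is that visit, contradicting the pre-baseline diary in Sections 4.1, 4.1.1 and 7.6.1

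*Combined protocol and SAP*

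**What the plan says.** The instruction in question:

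- Section 7.1.2.2 opens with "The following assessments will be performed at the Baseline visit" and includes, under Raynaud attacks, "participant provided the one-day diary and RCS to complete the day following the screening". The same list has the participant try the device for up to 30 minutes at that visit.

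The sections that place the baseline diary earlier:

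- Section 4.1 defines a one-week observation period with a daily diary: "This will occur in the seven days preceding the baseline intervention phase".
- Section 4.1.1, under screening: "Participants will be given the 7-day diary to be completed starting one week prior to their scheduled baseline visit", with a reminder by call or text.
- Section 7.6.1: "The diary is to be completed by participant for one-day during the observation period". Earlier in the same section the diary runs for seven days.
- Section 2.1 describes one-day use of a Raynaud application at baseline and at two weeks.

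Timing of visits and device:

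- Section 7.1.2.1 has screening evaluations performed and "information obtained up to 28 days before the baseline visit". Its list contains no diary hand-out.
- Section 4.1 also says: "The screening and baseline visits can be combined when the screening is not able to be performed over the phone in advance".
- Section 4.1.2 has the Raynaud condition score and Raynaud visual analog scale completed at the baseline visit before the device is given. It then says: "Participants will be able to use the device from the time they leave the visit". The end-of-study paper diary is issued before the participant leaves that visit.
- The schedule in Section 7.1 marks the diary at Visit 1, with a footnote marker whose text does not appear, and at Visit 2. The observation column is blank. Section 7.1.2.3 lists diary collection at Visit 2; no visit list has a collection at Visit 1.

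**The concern.** Taken as written, the Section 7.1.2.2 line asks for something that cannot be done when screening and baseline are separate visits: a form handed over at Visit 1 cannot be filled in on an earlier day. Staff would have to depart from either the date or the hand-out. If they keep the hand-out, the form is completed once the participant has the device.

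The study has no control arm, so each participant's own baseline is the only comparator. Raynaud improvement is a named secondary objective. Three of the six components of the Raynaud composite in Section 7.6.1 depend on the diary for their baseline: attack symptoms, attack duration and number of attacks per day. If some participants keep the diary before the device and others after it, the baseline mean mixes two different quantities.

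**Working it through.** The plan gives no figure on this point to reproduce, so the check is one of dates.

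**Inputs.** Visit 1 is day 0. Screening is day −g, with g from 1 to 28 for separate visits (Section 7.1.2.1) and g = 0 for combined visits (Section 4.1). The observation week is days −7 to −1 (Section 4.1). The device is available from the end of Visit 1 (Section 4.1.2).

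**Step 1: the day the line names.** The day after screening is day −g + 1 = 1 − g.

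- It is already past at Visit 1 when 1 − g < 0, that is g ≥ 2: 27 of the 28 separate-visit gaps.
- At g = 1 it is day 0, Visit 1 itself.
- At g = 0 it is day +1, when the participant already has the device.

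**Step 2: where that day falls by calendar.**

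- Inside the observation week when −7 ≤ 1 − g ≤ −1, that is g = 2 to 8: 7 gaps.
- Before the observation week when 1 − g < −7, that is g = 9 to 28: 20 gaps.
- Check: 7 + 20 = 27, as in step 1.
- Counting only gaps that leave room for a full seven-day diary (g = 7 to 28, 22 gaps), 2 fall inside (g = 7 and 8) and 20 before.

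These are counts of permitted gaps. The documents say nothing about how often each gap will occur.

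**Step 3: what a Visit 1 hand-out permits.** A form first received on day 0 cannot be completed prospectively on any day from −7 to −1, whatever g is.

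**Step 4: which text staff would work from.** The timing note after the schedule refers the reader to Section 7. There, Visit 0 has no hand-out, the schedule's observation column is blank, and Visit 1 provides a diary but does not collect one. The hand-out that works, in Section 4.1.1, is not carried into the visit lists.

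**Step 5: possible bias.** Let D be the true mean change, p the fraction of participants whose baseline diary is completed after the device is available, and s the share of D already present on that day. The baseline mean moves by p × s × D, so the estimated change is D × (1 − p × s). The documents give neither p nor s. With each anywhere from 0 to 1, the shrinkage runs from 0% to 100%, so the formula shows the mechanism and gives no estimate.

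**The case against.** The strongest reply is that one line does not override the rest of the protocol. For separate visits, Sections 4.1, 4.1.1 and 7.6.1 all place the diary before the device, and Section 4.1.1 adds a reminder. The line can also be read as referring to a diary given earlier, at screening. On that reading nothing is recorded after Visit 1 and only the date conflicts. This stands: the harm is conditional on Section 7.1.2.2 being followed as a Visit 1 hand-out.

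Three stronger readings are tempting, and the documents do not support them.

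- A reader might infer that the trial's Raynaud baseline will be recorded on the device. Other sections provide a pre-device diary, and use is at the participant's discretion, so the form would be completed with the device available, not necessarily in use.
- A reader might turn 20 of 28 or 20 of 22 into a proportion of participants with a spoiled baseline. That needs an assumed distribution of gaps. Moreover, days before the observation week are pre-device and cause no dilution of the change.
- A reader might cite the protocol's statements on speed of action as evidence of a first-day Raynaud effect. In Section 1.2 the near-immediate effect concerns autonomic tone, and the effect within days concerns fatigue and energy. Neither reports a change in Raynaud attacks.

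It is also fair that only secondary outcomes are involved, and that Section 8.1 calls the analysis largely descriptive and hypothesis-generating.

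The reply does not remove the contradiction. The visit-level text is what coordinators are likely to use, and it omits the hand-out that the other sections rely on.

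**Conclusion.** The point holds as an internal contradiction with a conditional consequence. With separate visits, Section 7.1.2.2 names a day that is past at Visit 1 for 27 of 28 gaps and is Visit 1 itself for the remaining one. This count assumes only that screening falls 1 to 28 days before baseline. If the line is applied as a Visit 1 hand-out, baseline attack frequency, duration and symptoms would be collected once the device is available, and the before-after change could be biased. If the device acts on that day in the same direction as later, the change would be understated. The size cannot be determined from the documents.

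The primary PROMIS-Fatigue endpoint, the sample size, and the condition score and visual analog scale completed at Visit 1 under Section 4.1.2 are not affected. The daily diary version of the condition score in Section 7.6.1 would share the problem. The text should be corrected because the correction is cheap and protects the only comparator for these outcomes; it does not call the main result into question.

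**What to change.** - In Section 7.1.2.2, replace the line with an instruction to collect and check the observation-period diary before the device is provided, including before the 30-minute trial use.
- In Section 7.1.2.1, list the diary hand-out at Visit 0, in line with Section 4.1.1. In the Section 7.1 schedule, mark the observation column and supply or remove the footnote.
- Keep the end-of-study diary hand-out at Visit 1, as in Section 4.1.2.
- In Section 8.2.2, state that only diary days dated before first device use count as baseline.
- Reconcile Sections 2.1 and 7.6.1 with this, including paper diary or application, one day or seven, and the two-week time point.

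The changes are to wording only, but they have a cost in data. A participant who forgets the diary has no baseline diary value. The same holds for every participant whose screening and baseline visits are combined, unless the device is provided after an observation period. Gaps of 1 to 6 days leave less than a full diary week. The plan should say how such participants enter the Raynaud analyses and report how many there are.

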7.1.2.3 Visits 2 (28 days + 3 days from the baseline)

- PROMIS-fatigue scale administered
- Patient reported outcomes (QUIDS-SR, patient global assessment, PROMIS-fatigue, PROMIS-29, HAQ- D1/SHAQ, visual analog scales) and physician global assessment
- Vital signs (blood pressure and heart rate).
- Assessment of Raynaud attacks – diary will be collected.
- Recording and assessment of AEs (see Section [7.5.1.3](#))
- Digital ulcer assessment

7.1.2.4 Unscheduled visit

Should participants report any difficulty or unexpected issues using the Apollo system at home, they will be able to contact research study staff to arrange for technical support or for an unscheduled (UNSCH) visit to the clinic for additional assistance. Technical support from study staff will be available to subjects within 24 hours of contacting study staff. Subjects will be provided with an email address and phone number for study staff upon enrollment in the study.

7.2 Population characteristics

7.2.1 Demographic

The following demographic data will be recorded:

- Date of birth (age)
- Sex
- Race and Ethnicity
- Alcohol consumption
- Smoking History
- Level of Education

7.2.2. Medical history

A 12-month medical record review will be requested from each subject prior to entering into the study. Medical history findings (i.e., previous diagnoses, diseases or surgeries, medications, etc) meeting all criteria listed below will be collected:

- Considered relevant to the study
- Medical history related to concomitant therapy

7.3 Efficacy

Primary efficacy outcome measure:

- Change from baseline to end of study on the PROMIS-Fatigue scale.

Secondary efficacy measures during double-blind period:

- HRQOL using PROMIS-29
- Physical function as assessed by HAQ-DI, and HDIIS-DU
- Visual analog scales from scleroderma-health assessment questionnaire (SHAQ) assessing burden of digital ulcers, Raynaud's disease, gastrointestinal involvement, breathing, and overall disease
- QUIDS-SR
- Improvement of Raynaud's phenomenon
 - Raynaud's condition score
 - Number of Raynaud's attacks/day
 - Patient and physician assessment of RP; pain, numbness, and tingling during an RP attack; and duration of attacks
- Patient's and physician's global assessment on a Likert scale
-

7.5 Safety**7.5.1 Adverse events**

The Apollo system has been tested and independently validated by individual members of a number of different institutions in the military and many Veterans, several academics at Universities, >10 elite athletics clubs, in pediatric clinics, nursing homes, as well as in two University of Pittsburgh clinical trials with 6 more trials currently underway. The Company has over 2000 beta testers and has conducted over 500 long-term case studies with consistent results. The technology proposed here has also been tested in children (as young as 4yo), geriatric users, and other extremely vulnerable populations (such as those with treatment-resistant PTSD) without any reported adverse reactions.

Participants will be informed about any and all potential risks. There are no known long-term risks to the subjects from any of the study procedures, which have been used safely on thousands of men, women, and children. All study personnel examine screening materials before asking the participant to engage in any of the study activities in order to minimize the risks associated with the study procedures. If any additional physiological or mental health conditions are revealed during the screening or enrollment, they will be discussed individually with the clinical team ([name] et al.) prior to officially enrolling the subject in the study. If results are best discussed with the participant's physician, the participant will be offered the opportunity to complete a release of information form allowing [name] to contact the participant's physician directly.

Should any adverse events be detected/reported/observed by subjects or study staff, subjects may easily discontinue use of the Apollo system immediately either by:

- 1) Turning the wearable off with the buttons on the device or
- 2) Removing the wearable from their body

7.5.1.1 Definitions**Definition of adverse event****(AE)**

In a clinical study, an AE is any untoward medical occurrence (i.e., any unfavorable and unintended sign [including abnormal laboratory findings], symptom or disease) in a patient or clinical investigation participant after providing written informed consent for participation in the study. Therefore, an AE may or may not be temporally or causally associated with the use of a medicinal (investigational) product.

A surgical procedure that was planned prior to the start of the study by any physician treating the participant should not be recorded as AE (however, the condition for which the surgery is required may be an AE).

In the following differentiation between medical history and AEs, the term “condition” may include abnormal physical examination findings, symptoms, diseases, laboratory results, and ECG findings.

- Conditions that started before signing of informed consent and for which no symptoms or treatment are present until signing of informed consent are recorded as medical history (e.g., seasonal allergy without acute complaints).
- Conditions that started before signing of informed consent and for which symptoms or treatment are present after signing of informed consent, at *unchanged intensity*, are recorded as medical history (e.g., allergic pollinosis).
- Conditions that started or deteriorated after signing of informed consent will be documented as AEs.

Definition of serious adverse event (SAE)

An SAE is classified as any untoward medical occurrence that, at any dose, meets any of the following criteria (a – f):

- a. Results in death
- b. Is life-threatening

The term ‘life-threatening’ in the definition refers to an event in which the participant was at risk of death at the time of the event, it does not refer to an event which hypothetically might have caused death if it were more severe.

- c. Requires inpatient hospitalization or prolongation of existing hospitalization

A hospitalization or prolongation of hospitalization will not be regarded as an SAE if at least one of the following exceptions is met:

- The admission results in a hospital stay of less than 12 hours
- The admission is pre-planned
(i.e., elective or scheduled surgery arranged prior to the start of the study)
- The admission is not associated with an AE
(e.g., social hospitalization for purposes of respite care).

However, it should be noted that invasive treatment during any hospitalization may fulfill the criterion of ‘medically important’ and as such may be reportable as an SAE dependent on clinical judgment. In addition, where local regulatory authorities specifically require a more stringent definition, the local regulation takes precedence.

- d. Results in persistent or significant disability / incapacity

Disability means a substantial disruption of a person's ability to conduct normal life's functions.

- e. Is a congenital anomaly / birth defect
- f. Is another medically important serious event as judged by the investigator

7.5.1.2 Classifications for adverse event assessment

All AEs will be assessed and documented by the investigator according to the categories detailed below.

7.5.1.2.1 Seriousness

For each AE, the seriousness must be determined according to the criteria given in Section [7.5.1.1](#).

7.5.1.2.2 Severity

The severity of an AE is classified according to the following categories:

- Grade 1 Mild
- Grade 2 Moderate
- Grade 3 Severe
- Grade 4 Very Severe
- Grade 5 Death

7.5.1.2.3 Causal relationship

The assessment of the causal relationship between an AE and the administration of treatment is a clinical decision based on all available information at the time of the completion. The assessment is based on the question whether there was a "reasonable causal relationship" to the study treatment in question.

Possible answers are "Related" or "Not Related" An assessment of "Not Related" would include:

1. The existence of a clear alternative explanation, or
2. Non-plausibility, e.g., the participant is struck by an automobile when there is no indication that the drug caused disorientation that may have caused the event; cancer developing a few days after the first drug administration.

An assessment of "Related" indicates that there is a reasonable suspicion that the AE is associated with the use of the study treatment.

Important factors to be considered in assessing the relationship of the AE to study treatment include:

- The temporal sequence
- Recovery on discontinuation (de-challenge), recurrence on drug re-introduction (re-challenge):
- Underlying, concomitant, intercurrent diseases:
 - Concomitant medication or treatment: The other drugs the participant is taking or the treatment the participant receives should be examined to determine whether any of them may be suspected to cause the event in question.

Causal relationship to protocol-required procedure(s)

The assessment of a possible causal relationship between the AE and protocol-required procedure(s) is based on the question whether there was a “reasonable causal relationship” to protocol-required procedure(s).

Possible answers are “yes” or “no”

